9.4 Interim Analyses

Interim review of recruitment will occur at the 6 month period, and interim analysis of preliminary data will occur at the 1 year mark. Sample size estimates will be reassessed given actual rates of enrolment after the 6 month period to ensure that the a priori sample size calculated is realistic, and the trial may be extended to allow for adequate patient recruitment. The trial will not be stopped for superiority reasons unless the adverse event rate and safety of the product is determined to be significant. Significance of the primary outcome will be assessed with an interim stopping level of $p=0.001$ using the Peto approach. (23)

10 DATA MANAGEMENT

10.1 Data Collection

Study data will be collected by study investigators using paper and electronic study data collection forms, the hospital based patient electronic medical record, and managed using REDCap electronic data capture tools hosted at Royal North Shore Hospital. REDCap (Research Electronic Data Capture) is a secure, web-based application designed to support data capture for research studies, providing: 1) an

intuitive interface for validated data entry; 2) audit trails for tracking data manipulation and export procedures; 3) automated export procedures for seamless data downloads to common statistical packages; and 4) procedures for importing data from external sources. (19) Photos of patients wounds will be uploaded to REDCap using the image upload survey tool, and should be taken from 20-30cm above the wound with a mobile phone utilising the REDCap mobile phone app. Wounds will not be marked or identified with unique patient identifiers, so care must be taken to ensure the photo is uploaded for the correct patient.

10.2 Data Storage

All electronic data will be stored on the secure online REDCap database at Royal North Shore Hospital. Only investigators and study staff will have their own password for access to this database. Passwords for the logins must not be shared, every person intending to enter data must contact the study coordinator at Royal North Shore Hospital to obtain their own log in. Any physical data will be stored within a locked room within the Research Units at each site and only study investigators will have access to this room.

10.3 Data Confidentiality

Re-identifiable coded data will be stored on our secure online REDCap database, accessible only by study investigators. Each site will be able to see only their own data except for Royal North Shore Hospital who will be managing the data. Relevant codes will be encrypted and stored on a hard drive in a locked room within Research Units at each site and only investigators will have access this room. The method of coding and data abstraction will be site specific, but controlled by the study investigators at RNSH.

10.4 Study Record Retention

After analysis of this data and the end of patient follow-up all electronic data from Royal North Shore Hospital, Royal Prince Alfred Hospital and Westmead Hospital will be stored securely at Royal North Shore Hospital in the Vascular Surgery Research Office and destroyed after 15 years in accordance with the Australian Code for the responsible conduct of Research, TGA ICH – GCP and the National Statement on Ethical conduct in Human Research.

11 ADMINISTRATIVE ASPECTS

11.1 Independent HREC approval

This study has been approved by the Sydney Local Health District HREC, reference number: X18-0513

11.2 Amendments to the protocol

Any amendments will be submitted to the HREC for review prior to implementation as per HREC guidelines.

11.3 Protocol deviations

Any protocol deviations will be submitted to the HREC for review.

11.4 Participant reimbursement

Participants will not be reimbursed in this study.

11.5 Financial disclosure and conflicts of interest

Nil disclosures or conflicts of interest

12 USE OF DATA AND PUBLICATIONS POLICY

Intention is to publish study results in a peer-reviewed academic journal. Study participants will be informed that academic journals are accessible to the public, and all published patient data associated with this study will be de-identified to ensure patient confidentiality.

14 APPENDICES (A – G)

Appendix A. Classification of wound complications (adapted from Mehrabi et al (3), CDC guidelines; Horan et al (17))

1) Superficial wound dehiscence: A separation of the superficial layers (skin and subcutaneous tissues) in the absence of documented incisional infection.

(2) Deep wound dehiscence or fascial dehiscence: The separation of the muscular fascia of the incision in the postoperative period, requiring operative repair.

(3) Perigraft fluid collection/seroma: detected by clinical suspicion and confirmed by ultrasound or CT/MRI. Perigraft fluid collections are diagnosed when the location of the fluid is deep to the muscular fascia. A seroma is diagnosed when there is a sterile fluid collection superficial to the muscular fascia. Urine leaks are also recorded, and fluids can be identified through pathology testing.

(4) Superficial wound infection: Diagnosed within 30 days of operation, limited to skin or subcutaneous tissue, and at least one of the following should be present:

- (a) purulent drainage from the superficial incision;
- (b) a sign or symptom of infection, such as pain, tenderness, heat, or swelling.
- (c) the diagnosis of superficial wound infection is confirmed by the surgeon.

(5) Deep wound infection: Diagnosed within 30 days of operation, involvement of the fascial or

muscular layers, and at least one of the following should be present:

- (a) purulent drainage from the deep incision;
- (b) spontaneous dehiscence while the patient has fever (>38_C), localized pain, or tenderness;
- (c) An abscess is found on direct examination, on reoperation, or by radiologic examination; the content contains pus, and the culture yielded one or more micro-organisms;
- (d) the diagnosis of deep incisional infection is confirmed by the surgeon.

(6) Cellulitis: Diagnosed by presence of erythema, tenderness, swelling and warmth of the skin surrounding the wound.

(7) Lymphocele: Deep lymphatic collections with pseudomembrane formation. The diagnosis is made by ultrasonography, CT or MRI and confirmed by needle aspiration of the lymphocele content and measuring the creatinine concentration or finding lymphatic components.

(8) Prolonged wound drainage: Defined as continuous fluid discharge greater than 50 mL/d through the drain or wound for more than seven days after transplantation during the first hospitalization. Fluids are identified by pathological testing at clinician discretion

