2. INTRODUCTION AND BACKGROUND

2.1 Background Information

Renal transplantation is considered to be the best treatment option for patients with end stage kidney disease in terms of quality of life and survival outcomes, as well as relative cost efficiency compared to dialysis.(1) Transplant recipients are susceptible to wound complications, arguably the most common post-transplant surgical complication, which may contribute to an additional risk of graft rejection or failure, prolonged length of stay, readmission and re-operation, as well as increased treatment costs. (2)

Wound complications have been previously superficial or deep dehiscence and/or infection, perigraft collections or seromas, cellulitis, lymphocoeles, and prolonged wound drainage. Studies have shown that the most important risk factors for wound complications in transplantation are immunosuppression and obesity (3). The incidence of wound infection in the presence of immunosuppression is approximately 7%, and more potent immunosuppressive agents are thought to result in a higher incidence of wound complications. (4) Comparing patients with high (>30) and low BMI (<30) patients, meta-analyses have demonstrated a significantly higher risk of wound infection (RR = 3.13, CI, 2.08–4.71; P <0.001), and wound dehiscence (RR 4.85, CI, 3.25–7.25; P <0.001). (5)(6)

Other relevant factors in renal transplantation include surgical technique and expertise, reoperative procedures, the presence of a haematoma, as well as recipient comorbidities such as advanced age, diabetes, malnutrition, dialysis (haemo- and peritoneal), and prolonged uraemia. The surgical closure technique of the incision, in particular, the precise closure of defects in each layer, has also been identified as an independent factor in reducing wound complications. (7) (8)

Negative pressure wound therapy (NPWT) utilises a foam sponge, in combination with a semipermeable adhesive dressing and a vacuum pump device to increase blood flow, drain fluid and exudate, and contract wound edges. Meta- analyses have suggested that when compared to standard wound dressings on closed incisions, NPWT significantly decreases wound size and healing time, with a significant reduction of risk of surgical site infections (RR=0.54, p= 0.01), and a significant reduction in risk of seroma formation (RR=0.48, p=0.01). (9) (10) (11).

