4.6 Primary and Secondary Outcome Measures

Primary outcomes of this study include wound infection, wound dehiscence or fluid collection at the surgical site within 30 postoperative days (see Appendix for Classification of wound complications)

Secondary outcomes include pain, scar healing, quality of life, reoperation, duration and volume of wound drainage, graft function, hospital length of stay, clinical adverse events and mortality (see Appendix for NRS, POSAS, EQ 5D-5L and List of dependent variables).

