9.3 Statistical Analysis Plan

Statistical analysis will be pre-specified and conducted according to both principles of intention to treat and per-protocol analysis, using SPSS version 20 (IBM, Armonk, NY, USA). Each incision will be randomized to the Prevena or standard dressing group. In the case that a patient requires bilateral incisions, both incisions will be allocated to the same treatment arm and counted as a single incision. Baseline characteristics of the two groups will be recorded and compared using Student's t-test and chi-square test for continuous and discrete data respectively. The primary outcome, the proportion of wound complications, will be compared between the Prevena and standard dressing groups using a chi-square test without Yates' continuity correction with a two-sided alpha of 0.05 at the final analysis using the Peto approach to preserve the overall significance level of 0.05 (23). An absolute risk increase/reduction for wound complications will be presented for the use of Prevena, as well as the number needed to treat in order to prevent specific wound complications. Patients lost to follow-up will be used in an intention-to-treat analysis with last observation carried forward.

The secondary outcome of identification of risk factors for wound complications will be assessed by multiple logistic regression of collected variables to assess their odds ratio. To prevent overfitting with the selected sample size, variables will be stepwise selected and also assessed for multicollinearity with the significance level of the dependent variables adjusted for multiplicity. Secondary outcomes will be compared between groups using a chi-square or Fisher's test for reoperation rate and delayed graft function and t-test for continuous variables, including the pain scale and quality of life. Non-normally distributed continuous variables will be tested for and compared using the Mann-Whitney *U* test. Survival analysis will be performed for allograft survival time with subjects without events censored at the 90 day final observation. A *p* value of less than 0.05 will be considered significant for the secondary outcomes and all tests will be two-sided.

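### Superficial dehiscence is counted only in uninfected wounds, so its between-arm comparison and NNT may be biased against Prevena if wounds spared infection still separate

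*Combined protocol and SAP*

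**What the plan says.** Appendix A item (1) defines superficial wound dehiscence as "A separation of the superficial layers (skin and subcutaneous tissues) in the absence of documented incisional infection". Item (2), deep dehiscence, is "The separation of the muscular fascia of the incision in the postoperative period, requiring operative repair" and carries no infection exclusion. Superficial infection, item (4), needs only one of three criteria. One of these is "a sign or symptom of infection, such as pain, tenderness, heat, or swelling"; another is confirmation by the surgeon.

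Section 4.6 states: "Primary outcomes of this study include wound infection, wound dehiscence or fluid collection at the surgical site within 30 postoperative days". Section 9.3 analyses a single proportion: "The primary outcome, the proportion of wound complications, will be compared between the Prevena and standard dressing groups". It then adds an absolute risk difference "as well as the number needed to treat in order to prevent specific wound complications".

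The available text has no rule for a superficial wound that is both separated and infected beyond the exclusion in item (1), and it plans no analysis of separation regardless of infection. The wound form in Appendix B records skin separation as an item of its own, with no condition on infection.

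**The concern.** Item (1) makes one outcome depend on the absence of another that occurs after randomisation. Section 2.1 cites a meta-analytic risk ratio of 0.54 for surgical site infection with negative pressure therapy, so the excluding event should be rarer in the Prevena arm. A separated, infected wound in the control arm counts as infection only. If Prevena prevents that infection but the wound still opens, the same separation counts as superficial dehiscence. The two arms are then filtered differently, and randomisation no longer protects the comparison of this class.

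At stake is one component row and its NNT. A device that leaves separation unchanged could show a risk ratio above 1 and a number needed to harm. The filter also rests partly on judgement by unblinded staff: section 5.4 leaves the surgical team unblinded, and item (4) accepts a single sign or the surgeon's confirmation.

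**Working it through.** **The plan's own figure.** Section 9.1 gives 239 per group for 15% v 7%. With its formula and rounded z values: (1.96·√(0.11·0.89·2) + 0.84·√(0.15·0.85 + 0.07·0.93))² / 0.08² = 238.7, so 239 is reproduced. This is a calculation for the composite. A wound that is separated, infected or both counts once in the composite under either definition, so neither the primary test nor the 239 changes.

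**Inputs for the component.**
- r = 0.54, infection risk ratio (section 2.1).
- s = control proportion with any superficial separation. Not given. The audit dehiscence rates in section 9.1 (5% at Site 1, 18% at Site 3) are used as a range, although the plan does not say that those events were superficial.
- q = share of control separations with documented infection. Not given; 10% to 75% is shown.
- m = share of separated wounds spared infection that still separate. Not given; 1, 0.5 and 0 are shown.

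**Formulas.** Control rate in the item (1) class: s(1−q). Prevena rate: s(1−q) + m·s·q·(1−r). Ratio: 1 + 0.46·m·q/(1−q). The ratio does not depend on s.

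| q | m = 1 | m = 0.5 | m = 0 |
|---|---|---|---|
| 10% | 1.05 | 1.03 | 1.00 |
| 25% | 1.15 | 1.08 | 1.00 |
| 50% | 1.46 | 1.23 | 1.00 |
| 75% | 2.38 | 1.69 | 1.00 |

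**Absolute size at m = 1, q = 50%.** The difference is 0.46·s·q. For s = 5%, 10% and 18% it is 1.15, 2.30 and 4.14 percentage points, an apparent number needed to harm of about 87, 43 and 24.

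**Chance of a nominally significant false signal** (m = 1, s = 10%, 250 per arm). Expected events, control v Prevena, are 22.5 v 23.7, 18.8 v 21.6, 12.5 v 18.3 and 6.2 v 14.9 for the four values of q. The chance of significance is about 4%, 7%, 19% and 48%. At q = 50% it is about 11% for s = 5% and 31% for s = 18%.

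**If Prevena also reduces separation.** Let u be the true risk ratio for any separation. The answer depends on how 0.54 is applied.
- (a) To the infected share among separated wounds: ratio = u(1−0.54q)/(1−q).
- (b) To the rate of infected separations: ratio = (u−0.54q)/(1−q).

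At q = 50%:
- u = 0.75: (a) 0.75·0.73/0.5 = 1.10; (b) (0.75−0.27)/0.5 = 0.96.
- u = 0.50: (a) 0.50·0.73/0.5 = 0.73; (b) (0.50−0.27)/0.5 = 0.46.

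Under (a) the ratio exceeds 1 unless u is below 0.95, 0.87, 0.69 or 0.42 for q = 10%, 25%, 50% or 75%. So at u = 0.50 only the 75% case exceeds 1 under (a): 0.50·0.595/0.25 = 1.19. Under (b) that case gives (0.50−0.405)/0.25 = 0.38.

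**Check of the remedy.** Counting all separations at m = 1 and s = 10% gives 10.0% v 10.0%, ratio 1.00. Item (1) gives 5.0% v 7.3% on the same wounds at q = 50%.

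**The case against.** The strongest reply is that the shift is conditional. If infection causes the separation, preventing one prevents the other and no wound changes class. Appendix A item (5)(b) itself treats spontaneous dehiscence with fever, pain or tenderness as a criterion of deep infection, so a causal link is plausible. Section 9.1 also plans on roughly a 50% reduction in all wound complications. If separation falls by about that much, the component stays favourable at 50% infected (0.46 to 0.73), and under convention (b) there is essentially no artefact. Uninfected dehiscence is a legitimate class taken from published schemes, and section 9.3 names no test for it.

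Most of this stands, and it limits the point. A reader might infer that the dehiscence result will necessarily turn against Prevena. The documents do not support that: they give neither the infected share nor the share of spared wounds that still separate, and a ratio above 1 needs Prevena to act more on infection than on separation. A reader might also carry the point over to dehiscence as a whole or to the site audit rates. The exclusion is in item (1) only, and section 9.1 does not say that the audits used Appendix A.

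The reply does not remove the dependence on a post-randomisation event, and nothing in the plan corrects it. A class suited to description is not thereby suited to a between-arm NNT.

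**Conclusion.** The point holds for the superficial-dehiscence component and its NNT: these may be biased against Prevena. With no true effect on separation, the apparent risk ratio runs from 1.05 to 2.38 for infected shares of 10% to 75%. It falls to 1.03 to 1.69 if half of the spared wounds still separate, and to 1.00 if none do. With a true 25% reduction in separation and 50% infected, it is 0.96 to 1.10 depending on how 0.54 is applied. With a reduction of about 50% at that infected share, it stays below 1. A misleading point estimate is more likely than a significant false harm signal, unless the infected share is large.

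It would be wrong to infer that the primary result is biased. The composite counts the same patients under either definition, and the sample size and deep dehiscence are untouched. This is a component-level reporting matter, worth correcting because the correction is cheap.

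**What to change.** In section 9.3, state that the between-arm comparison and NNT for superficial separation count every superficial separation within 30 days, whether or not infection is present. Let a patient count in both the separation and infection rows, but only once in the composite. Show separation without infection descriptively, with no NNT. The Appendix A class can stay as a descriptive label. Also state which categories of the skin item on the Appendix B form count as superficial separation.

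The cost is a sentence or two of analysis text. The form already records skin separation, and infection status is needed for the primary outcome anyway. The form has no single field for infection as Appendix A defines it, and Appendix C was not in the text available, so the source of the infection row should be named. The sample size, visits and clinical management do not change. The one small downside is that component counts will no longer add up to the composite; a table footnote can say so.

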The intervention arm will have the closed incision dressed with the Prevena Incision Management System (Kinetic Concepts Inc, San Antonio, TX, USA), a portable NPWT device, utilising a foam interface containing 0.019% ionic silver. The Prevena is preset to a continuous vacuum suction at 125mmHg. The Prevena device of appropriate size is to be applied under sterile conditions at the time of closure of the incision, with drain placement to be >10cm from the wound edge. The device should remain intact for a total of 7 days, at which point it will be removed. The wound will be inspected by a study investigator for evidence of a wound complication. A dressing may be reapplied, including a Prevena dressing if thought clinically indicated by the presence of a wound complication.

Postoperative ultrasound of the grafted kidney may be performed by peeling back the adhesive component of the Prevena dressing, and the Prevena can be subsequently reinforced with an adhesive dressing to establish adequate seal, with suction reinitiated within one hour if lost. If the wound edge is exposed, the Prevena device is inadvertently removed during ultrasound or clinician concern regarding the wound or device results in removal of the Prevena device earlier than planned, the device can be replaced at investigator discretion, however these details must be documented in the database. The patient will continue in the intervention arm as per principles of intention to treat regardless of whether the Prevena is replaced.

The control arm will have the closed incision dressed with a standard waterproof, adhesive dressing at the operator's discretion. This will not be controlled, but the type of dressing used will be recorded. This dressing will remain intact for a minimum of 7 days and may be changed thereafter as per site specific practices, which will be documented.

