Appendix B: Modified ASEPSIS Wound assessment form

Wound Assessment for patient Study ID _____ (de-identify patient to assessor)

Assessor _____

Wound site (please circle): Right Iliac Fossa/ Left Iliac Fossa/ Midline

Wound Length _____

Dressing type _____ (blinded to assessor)

Day _____ post op	points
Date /Time _____	
Skin  Intact  Minor/small separation or wound breakdown  Major / complete wound breakdown	
Separation of Deep Tissue  0% of wound affected	0

 1-20%  20-39%  40-59%  60-79%  >/= 80%	2 4 6 8 10
Fascia intact  Yes  No	
For Wound Dehiscence Size: length x width x depth (mm) _____	
Signs of Inflammation	
Erythema  0%  1-20% of wound affected  20-39%  40-59%  60-79%  >/= 80%	0 1 2 3 4 5
Pain at wound site  Yes  No	
Exudate  No (Dry)  Yes (Moist)	0
Exudate Colour  Serous (clear)  Sanguineous (bloody)  Serosanguinous (thin/pink)  Purulent (thick opaque/green/brown)	
If serous: Exudate volume  Scant (1-20% wound moist/ bandage moist)  Small/minimal (20-39%)  Moderate (40-59%)  Large (60-79%)  Very large/Copious tissue filled with fluid (>80%)	2 4 6 8 10
If purulent: exudate volume  Scant (1-20% wound moist/ bandage moist)  Small/minimal (20-39%)  Moderate (40-59%)  Large (60-79%)  Very large/Copious tissue filled with fluid (>80%)	2 4 6 8 10

Odour
 
 No odour
 
 Malodorous
	

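### The protocol does not say that the blinded wound assessment decides the primary event, and under Appendix A the unblinded surgeon's confirmation alone can make one

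*Combined protocol and SAP*

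**What the plan says.** **The endpoint.** Section 4.6 makes infection, dehiscence or fluid collection within 30 days the primary outcome and refers to Appendix A for the classification.

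**The criteria.** For superficial and for deep infection, Appendix A asks for any one criterion from a list, besides the timing and tissue-depth conditions.
- Item 4(c): "the diagnosis of superficial wound infection is confirmed by the surgeon".
- Item 5(d): "the diagnosis of deep incisional infection is confirmed by the surgeon".
- Item 4(b): "a sign or symptom of infection, such as pain, tenderness, heat, or swelling". No judge is named.
- Item 1, superficial dehiscence: "A separation of the superficial layers (skin and subcutaneous tissues) in the absence of documented incisional infection".
- Item 6, cellulitis: "Diagnosed by presence of erythema, tenderness, swelling and warmth of the skin surrounding the wound". Section 4.6 does not say whether cellulitis counts as infection.

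**Who knows the arm.** Section 5.4 states that surgeons, clinical staff and patients are unblinded. Section 5.5 accepts that study investigators can tell the arm up to Day 7 and probably at Day 14. When the Prevena comes off at Day 7, section 4.2 says: "The wound will be inspected by a study investigator for evidence of a wound complication". The same section has study investigators record re-presentations for the endpoints.

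**What is blinded.** Section 5.5 sends wound photos from Days 7, 14, 30 and 90 to a designated independent assessor who does not know the arm. It also blinds that assessor and the imaging staff at Days 30 and 90, and tells patients not to reveal their dressing to them. The Appendix B form is marked "de-identify patient to assessor", with dressing type "blinded to assessor".

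**The concern.** The protocol builds a blinded assessment but does not connect it to the endpoint. Section 5.5 gives its purpose only as better validity. Appendix B awards points but has no threshold and no link to the Appendix A categories. Section 9.3 compares proportions of wound complications without naming the source of the event.

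Two things are at stake. First, a judgement made with knowledge of the dressing can be enough for a primary event. If such calls differ by arm, they can produce a false benefit or a false harm, or hide a true effect. The chi-square test cannot correct this, and a larger sample does not remove it. Second, two analysts could count different events from the same records, and the choice between them could be made after the data are seen.

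**Working it through.** **Setting the sections side by side**

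| Question | Where one would look | What is there |
|---|---|---|
| Who decides the event? | 4.6, 9.3 | No one named |
| Can the surgeon's view suffice? | Appendix A, 4(c) and 5(d) | Yes, as one of three or one of four alternatives |
| Is the surgeon blinded? | 5.4 | No |
| Is there a blinded reading? | 5.5, Appendix B | Yes |
| Does it determine or override the event? | 4.6, 5.5, 9.3, Appendices A and B | Not stated |
| How is a disagreement settled? | Same places | Not stated |

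Removing 4(c) and 5(d) alone would not close the gap, because 4(b) also rests on clinical judgement with no blinded judge. Part of the composite is outside the point: collections rest on imaging, with imaging staff blinded, and deep dehiscence requires operative repair.

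**The plan's own figure.** Inputs from section 9.1: 15% v 7%, two-sided alpha 0.05, power 80%, 1:1, no continuity correction.

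N = {1.96 × √(2 × 0.11 × 0.89) + 0.84 × √(0.15 × 0.85 + 0.07 × 0.93)}² / 0.08² = (0.8673 + 0.3686)² / 0.0064 = 238.7, so 239 per arm, as stated.

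At 250 per arm the standard error is 0.0280 under the null (pooled) and 0.0278 under the alternative. Power = Φ((0.08 − 1.96 × 0.0280) / 0.0278) = Φ(0.906) = 81.8%.

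**Illustrations.** All error rates below are assumptions. Over-calling a fraction x of event-free patients changes a true rate p to p + (1 − p)x.

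1. *No true effect, 15% in both arms, over-calling of 4% control v 2% Prevena.* Observed rates are 0.15 + 0.85 × 0.04 = 18.4% and 0.15 + 0.85 × 0.02 = 16.7%. The difference is 0.017 and the standard error 0.0340. The chance of a false benefit is Φ((0.017 − 0.0667) / 0.0340) = Φ(−1.46) = 7.2%, against 2.5% with no over-calling. With the arms reversed, the same figure is the chance of a false harm.
2. *Range, over-calling in controls only, no true effect.* At 1%, 2%, 3% and 5% the chance of a false benefit is 4.5%, 7.5%, 11.7% and 24.2%.
3. *True 15% v 7%, over-calling of 2% control v 4% Prevena.* Observed 16.7% v 10.7%; power 49%.
4. *True 15% v 7%, equal over-calling of 2%, 5% or 10%.* Power 75%, 65% or 52%. This holds only if the planned 15% and 7% are free of over-calling.

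**What the remedy could cost in power.** Let f be the share of events that are adjudicated and m the fraction of those missed, equal in both arms. Observed rates become p(1 − f × m).

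| m | f = 0.3 | f = 0.7 | f = 0.9 |
|---|---|---|---|
| 10% | 80.4% | 78.6% | 77.6% |
| 20% | 79.0% | 75.0% | 72.7% |

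**The case against.** The strongest reply is that silence is not a rule. A reader might infer that the protocol ranks the surgeon above the blinded assessor, or gives the assessor no part in the endpoint. Neither is stated: Appendix A lists criteria, and section 5.5 plans the blinded reading to make assessment more valid. What remains is that the assessor's role is unstated while the surgeon's confirmation is an explicit sufficient criterion.

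A reader might also infer that the Day 30 review is unblinded, since section 4.2 gives it to a study clinician or the wound nurse consultant. That does not follow. Section 5.5 blinds the designated assessor at Day 30 and asks patients not to disclose their arm to that person, which suggests that the two meet. The Day 30 reviewer may or may not be the blinded assessor.

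Three further limits stand.
- Appendix C was not in the text available for this review, so a rule there cannot be excluded. The sections that cite it describe data collection, assessments and adverse events.
- The 15% draws on site audit data, and published reductions are cited for the treatment effect. If both planning rates reflect ordinary calling, equal over-calling is already in them and the power loss in illustration 4 disappears.
- A photo cannot show pain, tenderness, heat or deep-tissue signs, so a blinded reader still depends partly on bedside notes.

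That the surgeon criterion is adapted from published definitions does not answer the point, because its source does not make the person applying it blinded.

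**Conclusion.** The point holds in a limited form, with medium confidence. Under the text as written, an unblinded judgement alone can create a primary event, and nothing available says that the planned blinded assessment decides, or how a conflict is resolved. This affects superficial and deep infection, superficial dehiscence and, if counted, cellulitis.

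The size is hypothetical. The 7.2% chance of a false benefit rests on assumed over-calling of 4% v 2%; if calls are accurate and unbiased, the effect is near zero. A reader might go further and conclude that the trial will be biased towards Prevena, or that its power is about 52%. The documents give no error rates, so they support neither the direction nor the amount.

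**What to change.** State the following in section 4.6, section 9.3 and Appendix A, for the primary analysis only:

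- Superficial and deep infection, cellulitis (if counted) and superficial dehiscence are classified against Appendix A by the blinded assessor already planned in section 5.5, for every patient, so that missed events can be found as well as over-called ones.
- The assessor uses the scheduled photos, the Day 30 assessment, swab and imaging results, and bedside findings with arm and dressing redacted.
- Purulent drainage, culture-positive abscess and dehiscence with fever count as met when documented in the redacted record. An event resting only on 4(b), 4(c) or 5(d) counts only if the blinded assessor agrees.
- The assessor's classification stands if it differs from the treating team's.
- Events as called under the current Appendix A wording are reported as a sensitivity analysis.

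Say also whether the Day 30 bedside reviewer is the blinded assessor. Day 7 and Day 14 cases should stay with the site's own assessor: section 5.5 allows an alternative site only for Day 30 and 90 photos, and section 10.3 restricts each site other than the managing hospital to its own data.

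**Cost.** Wording in three places. The photo reading is already scheduled: 500 patients × 3 visits = 1,500 photos to Day 30. The new work is preparing redacted records, including for re-presentations, where no photo is scheduled. Some true events may be missed; under the assumptions in the table above, power would be about 73% to 80%. Only endpoint classification changes, not patient care.
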